3.0 Safety of the Device

We are asking the Board to make a non-significant risk determination.

The device is not approved or marketed.

The device does not pose a risk to participants under 21 CFR 812.3(m).

This investigational device is not:

- Intended as an implant and presents a potential for serious risk to the health, safety or welfare of a participant;
- Purported or represented to be for use supporting or sustaining human life and presents a potential for serious risk to the health, safety or welfare of a participant
- For a use of substantial importance in diagnosing, curing, mitigating or treating disease or otherwise preventing impairment of human health and presents a potential for serious risk to the health, safety or welfare of a participant or
- Otherwise presents a potential for serious risk to the health, safety or welfare of a participant.

Please see Response to January 15 New England IRB Letter, specifically Responses to Questions 5 and 6, for a full explanation of the device safety and comparison to other predicate devices. .

4.0 Inclusion and Exclusion Criteria:

Inclusion Criteria:

1. Male or female participants between 2 years and 6 years of age (inclusive), of all races.
2. Previously diagnosed with moderate or severe ASD by a licensed professional.

3. Participants may be receiving any behavioral intervention therapy (e.g., ABA, Floor Time) during the course of the treatment. The final statistical analysis will control for the participants receiving behavioral therapies in control and experimental conditions. We expect the majority of the participants in both control and experimental conditions to be receiving behavioral therapies. There is no known interactions or complications of tPBM with behavioral therapy.

4. Parents of participants must understand the nature of the study.
5. Parents of participants must sign an IRB- approved informed consent form before initiation of any study procedures.
6. Parents of participants must have a level of understanding sufficient to communicate with the investigator and study coordinator, and to cooperate with all tests and examinations required by the protocol.
7. Participant child experiencing a major psychiatric disorder will be allowed to participate in the study provided they do not meet any exclusionary criteria.
8. The participant child is willing to participate in this study.

Exclusion Criteria:

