1. Participant child is experiencing severe self-injurious behavior or severe aggressive behavior to self or others (within past 7 days).
2. Participant has been diagnosed with another psychiatric or neurological disorder (e.g. epilepsy) or have exhibited symptoms of major psychiatric disorders within the last 30 days.
3. Participant has an unstable medical condition (that requires clinical attention).
4. Participant has a significant skin condition at the procedure sites (i.e., hemangioma, scleroderma, psoriasis, rash, open wound or tattoo).
5. Participant has an implant of any kind in the head (e.g. stent, clipped aneurysm, embolised AVM, implantable shunt - Hakim valve).
- 6. Participant has receiving medication on a regular basis for Autism or any other medical condition.**
7. Any use of light-activated drugs (photodynamic therapy) within 14 days prior to study enrollment (in US: Visudine (verteporfin) - for age related macular degeneration; Aminolevulinic Acid- for actinic keratoses; Photofrin (porfimer sodium) - for esophageal cancer, non-small cell lung cancer; Levulan Kerastick (aminolevulinic acid HCl) - for actinic keratosis; 5-aminolevulinic acid (ALA)- for non-melanoma skin cancer).
8. Current treatment with a psychotropic medication.
9. Investigator and his/her immediate family, defined as the investigator's child or grandchild.

5.0 Sample Size:

30 children will be included in the study. We need at least 15 participants in the control condition, and 15 participants will receive a combined light and audio treatment therapy. These numbers will allow us to gain sufficient statistical power to detect small size systematic effect. **We anticipate to screen about 40 participants to recruit 30 participants for the study.**

We plan to screen more than 30 prospective children, because we expect some of them to be ineligible for the study, due to the above listed Exclusion Criteria. We plan to enroll 30 children, so that each group will have at least 15 participants. We do anticipate that some of the participants will withdraw, for various reasons. participant We will continue screening until we have 30 enrolled participants.

If a participant drops out of the Study we will attempt to replace that participant, using the same Eligibility Screening Criteria.

6.0 Research Locations:

[name]

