This is a private professional office, with a waiting room and a receptionist. There are several private rooms within the office.

The child will be led to a private room, which will have toys and books inside it. The caregiver and one of the researchers will be present in the room at all times.

[name]

This is a private professional office, with a waiting room and a receptionist. There are several private rooms within the office.

The child will be led to a private room, which will have toys and books inside it. The caregiver and one of the researchers will be present in the room at all times.

7.0 Procedures Involved:

7.1 Location: The study will use pre-test and post-test design. The entire study on the children will be done in the office. The weekly interview with the parent may be done either in office or by phone, as preferred by the parent.

7.2 Conditions: There are two conditions: placebo condition, and combined light and audio therapy treatment condition. The placebo control condition will listen to nursery rhymes. **The placebo control condition will wear the same device, however the lights are not going to be turned on. Otherwise, all experience for participants in control and experimental conditions will be identical.**

This study replicates and extends previous studies of photobiomodulation in children older than 5 years of age (Leisman et al, 2018).

7.3 Participants: The participants will be matched on age, gender and number of hours of therapy they receive independent from the study. The participants will be 24-71 month old children previously diagnosed with moderate or severe ASD. The experiment will use random assignment. We plan to use 30 participants (15 in each group). **We plan to screen about 40 participants (or fewer) to recruit the 30 participants for this study.**

7.4 Random Assignment: Random assignment will be achieved by using random number generator programs frequently used in research (such as random.org). Each participant is assigned a number. The list of 30 numbers is entered into the program, which creates a random sequence of 30 participants. Here is an example of the beginning of such list generated for 30 participants

1 – 23

2 – 25

1 – 12

2 – 15

1 – 21

2 – 5

1 – 19

2 - 9

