7.7 On-going Data Collection: Parents will be asked to keep a daily diary of the child's behavior, specifically – words spoken, comprehension of instructions, eye contact, his sleep pattern, number of tantrums, anxiety, social interaction and eating. Qualitative data will be collected through short weekly interviews with the parents. These interviews can take place either in [name] office during the child's treatment or by phone. During those weekly interviews, the parents will be asked questions about their children's responsiveness to language, number of words they can produce, eye-contact, anxiety, frequency of tantrums, eating, and difficulties falling asleep and sleeping through the night. Please see attached proposed script for the weekly call. The qualitative data will be used to further inform and supplement quantitative data (total CARS 2 scores).

The study will collect qualitative and quantitative data. The quantitative data will be the total CARS2 scores of the participants of both Control and Treatment groups, obtained before and after the study is done. Mixed Design Analysis of Variance will be used to analyze quantitative data. **In addition, we will collect Before and After Prefrontal cortex EEG from the control and experimental treatment groups to measure electrophysiological changes in Prefrontal cortex. after treatment. EEG data will be analyzed (using Time-Frequency analysis), and after baseline normalization, the data will be used in aggregate to compare conditions numerically. The between group comparison before the treatment will be conducted using between subject T-test for each brainwave . The between group comparison will be conducted after treatment for each brain wave using between subject t-test. In addition, for the treatment condition only Before and After comparison will be conducted, using within subject t-test.** In addition, we will obtain qualitative data from weekly parental interviews, during which we will ask participants' parents about their children's behavior (see attached protocol). Qualitative data will be used for information purposes and will supplement quantitative data.

7.8 Blinding of the Researcher: [name] (the PI) will not be present in the room when the child is receiving the treatment. She will not be aware what group each particular participant has been placed in. [name] will be conducting the pre and post-testing interviews, as well as the on-going weekly interviews with the parents.

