## Data Collection and Statistical Analysis

### Primary Analyses

The last author, a licensed psychologist experienced in the use of CARS in clinical practice, conducted blinded Before and After CARS ratings for all participants. The final CARS evaluations were performed immediately after the final treatment session. CARS scores were analyzed using the independent sample t-test. We compared the differences from the baseline between both groups, calculating both the average difference and 95% CI within each group and between groups.

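### Protocol 5.0 claims sufficient power for a small effect with 15 per group; under conventional assumptions power is about 8%, and 80% power needs about 1.06 SD

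*Protocol*

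**What the plan says.** Protocol 5.0 (Sample Size) sets the numbers: "We need at least 15 participants in the control condition, and 15 participants will receive a combined light and audio treatment therapy". It then says of them: "These numbers will allow us to gain sufficient statistical power to detect small size systematic effect". Neither that section nor any other part of the documents gives a significance level, sidedness, a target power, an SD, a pre/post correlation or a numerical effect.

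The analyses to which the claim would apply are:

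- **CARS2, protocol 7.7:** "Mixed Design Analysis of Variance will be used to analyze quantitative data", on total scores before and after treatment.
- **CARS, SAP Primary Analyses:** an independent-sample t-test, where "We compared the differences from the baseline between both groups".
- **EEG, protocol 7.7:** "The between group comparison will be conducted after treatment for each brain wave using between subject t-test", on data described thus: "after baseline normalization, the data will be used in aggregate to compare conditions numerically".

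Two other provisions could affect precision. Protocol 4.0, inclusion item 3, says: "The final statistical analysis will control for the participants receiving behavioral therapies in control and experimental conditions". Protocol 7.3 says: "The participants will be matched on age, gender and number of hours of therapy they receive independent from the study".

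Protocol 1.0 calls the trial an open-label feasibility study, but it also lists efficacy among the aims and states an efficacy hypothesis.

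**The concern.** The sentence credits the design with a property that two groups of 15 do not normally have. It is also the protocol's only statistical reason for 15 per group.

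A reader who trusts it would take a non-significant CARS2 or EEG comparison as evidence against even a small effect, and would not expect a significant estimate to be heavily inflated if the true effect were small. With 15 per group, both expectations would be mistaken.

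**Working it through.** **Inputs.** From the documents: 15 per group and 1:1 allocation (protocol 5.0 and 7.3). With two groups and two time points, the group-by-time test of the mixed ANOVA is the same as a t-test on change, with 15 + 15 − 2 = 28 df, so the protocol and SAP analyses coincide here. My assumptions: two-sided 5% (consistent with the SAP's 95% intervals), 80% target power, and small = 0.2 SD of the analysed score. The plan gives no power figure to reproduce.

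**Power.** The noncentrality is d / √(1/15 + 1/15) = 2.739 d and the critical value is t(0.975, 28) = 2.048. From the noncentral t distribution:

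| Difference, in SD of the analysed score | Power |
|---|---|
| 0.2 | 8.3% |
| 0.5 | 26.2% |
| 0.8 | 56.2% |
| 1.06 | 80.0% |

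For 80% power at 0.2 SD, 394 per group would be needed.

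**Could a feature of the plan or another reading rescue the sentence?**

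- *One-sided 5%:* power is 13.3% at 0.2 SD; 80% needs 0.93 SD.
- *Adjustment for behavioural therapy:* the effect becomes 0.2/√(1 − R²), with 27 df. R² = 0.5 gives 11.6%; 80% needs R² = 0.964.
- *Matching, analysed as 15 pairs:* the effect becomes 0.2/√(2(1 − ρ)), with 14 df. ρ = 0.5 gives 11.2%; 80% needs ρ = 0.967.
- *Small as 0.2 SD of the raw score, change analysed:* the effect in change SDs is 0.2/√(2(1 − r)). Setting this to 1.060 gives r = 1 − (0.2/1.060)²/2 = 0.982.
- *Small as interaction f = 0.1:* λ = 0.01 × 30 × 2/(1 − r), tested on F(1, 28). Power is 18% at r = 0.5, 39% at r = 0.8 and 66% at r = 0.9; 80% needs r = 0.929.
- *Post-treatment EEG t-tests:* again 8.3% at 0.2 SD of the value compared. Whether pre/post correlation helps depends on what the baseline normalization does, which the text does not settle.

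**Consequences for interpretation.** The half-width of the 95% CI for a between-group difference is 2.048 × √(2/15) = 0.748 SD. In a simulation of 4 million trials:

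- With no true effect, the upper 95% limit falls below 0.2 SD in about 5% of non-significant results, and below 0.5 SD in about 25%.
- With a true effect of 0.2 SD, significant estimates in the right direction overstate it by a median factor of 4.2 (middle half 3.7 to 4.8).

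**Context on the CARS scale (not a planning input).** The SAP's Primary Outcome section reports a 95% CI of 2.357 to 12.107 with 16 and 14 children. The SE is (12.107 − 2.357)/(2 × 2.048) = 2.380, so the SD of change is 2.380/√(1/16 + 1/14) = 6.50 points, and 1.06 SD is about 6.9 points. The minimal clinically important difference cited there is 4.5 points, or 4.5/6.50 = 0.69 SD, for which 15 per group gives about 45% power.

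**The case against.** Four points can be made for the plan.

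**Small is never defined, so no stated calculation is wrong.** True, and the 8% rests on a convention. But the conclusion does not hinge on 0.2 SD: even 0.5 SD of the analysed score has only 26% power.

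**This is a feasibility study.** That is a good reason to accept 30 children, and I do. It does not make an explicit, unqualified power claim correct.

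**The completed trial found a difference.** The SAP reports 7.23 points with its interval, so the imprecision is visible and the risk of misreading a null result did not arise for the primary CARS comparison. That limits the practical harm there. It says nothing about power for a small effect, and the risk remains for the EEG comparisons. The overstatement figure applies only if the true effect is 0.2 SD, which nothing in the documents establishes.

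**Calling the trial unpowered for moderate effects depends on the scale.** This is the strongest point. Interaction f = 0.25 reaches 80% power at r of about 0.55, and 0.5 raw SD at r of about 0.89. However, f = 0.25 at r = 0.5 is 0.25 × √(8/0.5) = 1.0 SD of change, which is not moderate on the analysed scale. The SAP's own SDs also imply a lower correlation. With 15 and 13 df, the pooled sum of the pre and post variances is 87.63 and the pooled value of twice the SD product is 86.70. Hence r = (87.63 − 6.50²)/86.70, about 0.52, assuming a common r in both groups. The wording about moderate effects therefore stands when tied to the SD of the analysed score, as it is below.

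**Conclusion.** The sentence is wrong as written. With 15 per group, a two-sided 5% test and small taken as 0.2 SD of the analysed score, power is about 8%, and 80% power requires about 1.06 SD. The significance level, the 80% target and the value of small are my assumptions because the protocol gives none. No alternative examined brings power for a small effect near 80%, unless the pre/post correlation is about 0.93 or more, the within-pair correlation about 0.97, or the variance explained by a covariate about 96%. The sample size, design and analysis are not in question. The correction should be made because this sentence alone supports the group size statistically and it misstates what a null or a significant result would mean.

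**What to change.** Replace the power sentence in protocol 5.0 with:

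> With 15 per group and a two-sided 5% test, the study has 80% power only for a between-group difference of about 1.06 SD of the analysed score (change score for CARS2) or larger; on that scale it is not powered for small or moderate effects.

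If the sponsor intends another significance level, state it and change the figure to match (0.93 SD for one-sided 5%). The cost is one sentence: no additional children, no new analysis and no design change. The only downside is a less favourable stated sensitivity.

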**Transcranial Photobiomodulation for
reducing autism symptoms in
children.**

October 1, 2020

PROTOCOL TITLE:

Transcranial photobiomodulation for reducing autism symptoms in children.

PRINCIPAL INVESTIGATOR:

Name	[name]
Department	N/A
Phone Number	

CO-INVESTIGATORS:

Name	[name]
Department	N/A
[contact]

Name	[name], CFA, Esq.
Department	N/A
[contact]

1.0 Purpose of the study:

The purpose of this 8-week open label feasibility study is to assess the tolerability, safety and efficacy of Transcranial LED Therapy for language learning and reducing symptoms of autism in children.

The investigators propose to enroll up to 30 participants of both genders ages 24 months to 6 years who have been previously diagnosed with moderate to severe ASD by licensed professionals according to the Diagnostic and Statistical Manual of Mental Disorders, Fifth Edition (DSM-5) criteria for Autism Spectrum Disorder (ASD).

The hypothesis to be tested is that exposure to photobiomodulation and speech parsing program will reduce children's symptoms of autism, such as delays in language production and comprehension, anxiety, tantrums, limited eye-contact and improve responsiveness.

2.0 Background / Literature Review / Rationale for the study:

2.1 Background Science of Photobiomodulation and Rationale:

There are several studies that suggest that mitochondrial energy disturbance is an underlying mechanism of autism, for at least some of the children. Specifically, Weisman, Kelley, Bauman, Cohen, Murray, Mitchell and Kern (2008) looked at the medical records of 25 children diagnosed with autism and found that "Levels of blood lactate, plasma alanine, and serum ALT and/or AST were increased at least once in 76%, 36%, and 52% of patients, respectively". Furthermore, 2 out of those 25 people had rare mtDNA mutations. The authors concluded that at least for a subset of ASD children, mitochondrial disturbances in energy production could be the underlying mechanism. Furthermore, Giulilvi, Zhang, Omanska-Klusek, Ross-Intra, Hertz-Picciotto, Tasson and Pessach (2010), looked at biochemical markers of ASD kids (2-5yo), and concluded that ASD children are more likely to have Mitochondria dysfunction, mtDNA replication and mtDNA deletion than neurotypical ones.

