We are developing a safe and effective protocol for administering tPBM via a wearable device. This physical device is getting developed by JelikaLite LLC. The parameters are developed by [name] (the PI of this study), [name] (leading photobiomodulation expert from Harvard Medical School and an advisor to JelikaLite), [name] (leading neuroscientist who is studying photobiomodulation at Boston Medical University and an advisor to JelikaLite), and [name] (an industrial product designer with over 30 years of expertise in designing medical devices). The purpose of this feasibility study is to evaluate the safety and comfort of the product, as well as preliminary efficacy of the treatment effect. The device will stimulate Default Mode Network (to increase brain connectiveness) as well as Broca and Wernike areas (to facilitate speech comprehension and production) and Occipital lobe (as many ASD children rely on visual information for language learning). The device will be physically light, comfortable to wear for children and could eventually be used at home as frequently as necessary.

The reason why the device may be helpful to children is because of the science of photobiomodulation. The device will have embedded LED lights in it, which will shine red light and near infra red lights. The children will wear the device for approximately 5-10 minutes, twice a week (closely replicating the protocol of Leisman et al as well as the clinical study at MGH). The light stimulates mitochondrial ATP production. Only about 2% of the light penetrates the skull. However, because brain is the largest energy consuming organ of the body, even those 2% result in significant

improvement of the symptoms (even small boost in ATP production results in significant improvement). Having more energy enables the brain cells to heal, grow and form new neural connections. Other benefits of tPBM is increased blood flow to the brain, which increase brain oxygen supply and reduce inflammation.

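### As written in 5.0 and 7.2, the CARS comparison tests light plus audio program as a package and cannot isolate the light effect; 7.5 leaves the control arm's audio in doubt

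*Protocol*

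**What the plan says.** **Content of the arms.** Protocol 5.0 says that "15 participants will receive a combined light and audio treatment therapy". Section 7.2 says: "There are two conditions: placebo condition, and combined light and audio therapy treatment condition. The placebo control condition will listen to nursery rhymes". It adds that controls wear the same device unlit, and then: "Otherwise, all experience for participants in control and experimental conditions will be identical". Section 9.0 lists the audio program, which it describes as input for language acquisition, as one activity and free play to nursery rhymes as another. It does not assign activities to arms.

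**Audio in 7.5.** This section has children hear the audio program while they wear the device, without distinguishing the arms. It also says that controls wear the device, switched off.

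**Stated aim.** The hypothesis in 1.0 is joint: "exposure to photobiomodulation and speech parsing program will reduce" symptoms. The purpose sentence in the same section names light alone: "assess the tolerability, safety and efficacy of Transcranial LED Therapy for language learning and reducing symptoms of autism in children". The title does likewise, and 13.0 tells parents that the study is meant to show what photobiomodulation does in young children with ASD. Section 2.2 sets out to "evaluate the safety and comfort of the product, as well as preliminary efficacy of the treatment effect" and explains the expected benefit this way: "The reason why the device may be helpful to children is because of the science of photobiomodulation". Section 7.2 adds: "This study replicates and extends previous studies of photobiomodulation in children older than 5 years of age". The available text of 2.1 and 2.2 argues for light and does not mention the audio.

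**Analysis.** The SAP (Primary Analyses) compares change in CARS between two groups with an independent-sample t-test. Under Primary Outcome it reports 7.23 (95% CI 2.357 to 12.107), then a responder analysis at 4.5 points, and then concludes that the treatment has clinically meaningful efficacy. The available SAP text names the groups Active and Sham and does not mention audio.

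**The concern.** On the plain reading of 5.0 and 7.2, two things change together between the arms: the light, and what the child hears. The audio program cannot be presumed inert, because 9.0 describes it as language input and delayed language is among the symptoms that the 1.0 hypothesis targets. There is no light-only or audio-only arm.

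At stake is what the main result may be said to show. A reader who comes from the title, the purpose sentence or 13.0 will take the CARS difference as evidence about photobiomodulation. With the plan followed as 5.0 and 7.2 describe it, the difference is evidence about a package. Section 7.5 leaves open whether controls heard the audio program after all, so the protocol alone does not settle which statement the data support.

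**Working it through.** **1. Reproduce the reported figure.** Inputs are from SAP, Primary Outcome: Active (n = 16) 43.5 before and 33.7 after; Sham (n = 14) 40.6 before and 38.0 after.

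- Difference in mean change: (43.5 − 33.7) − (40.6 − 38.0) = 9.8 − 2.6 = 7.2, consistent with 7.23 given rounded means.
- CI midpoint: (2.357 + 12.107)/2 = 7.232. Half-width: (12.107 − 2.357)/2 = 4.875.
- With t(0.975, 28 df) = 2.048, SE = 4.875/2.048 = 2.380. Then t = 7.232/2.380 = 3.04 and two-sided p = 0.005, which agrees with the stated 0.01 at two decimals.
- Responders: 14/16 = 87.5% and 5/14 = 35.7%, a difference of 51.8 percentage points.

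The reported difference is therefore sound as a contrast between the two arms. The question is what that contrast measures.

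**2. Set the arms side by side.**

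| | Active | Control by 7.2 | Control by 7.5 |
|---|---|---|---|
| Device worn | yes | yes | yes |
| Light | on | off | off |
| Audio | audio program | nursery rhymes | audio program |

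The natural reading gives the active arm the audio program throughout. Only the control arm's audio changes between sections. Section 9.0 fits 7.2, because it treats the two audios as different things.

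**3. Write down what each reading estimates.** Let L be the effect of light when the child hears nursery rhymes, A the effect of the audio program over nursery rhymes without light, and I any interaction.

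- Control by 7.2: contrast = L + A + I. There is one estimate for three unknowns, so L is not identifiable.
- Control by 7.5: contrast = L + I, the effect of light given on top of the audio program. The contrast then does address light.

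**4. Ask whether any planned analysis separates the components.** The t-test on change does not. The mixed-design analysis of variance in protocol 7.7 does not either: with two groups and two time points, its group-by-time term is the same contrast. The responder analysis compares the same two arms, so it has the same limit. Each of them tests the joint hypothesis in 1.0; none isolates light if the audio differed.

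**The case against.** **The strongest case on the other side.** The stated hypothesis is joint, so a package comparison is what the trial set out to make. The available SAP text makes no light-specific claim and concludes only about the treatment. The title and a line in a risk table do not define an estimand. The arm-by-arm text of 7.2 can reasonably govern the one general sentence in 7.5. The word at the start of "Otherwise, all experience for participants in control and experimental conditions will be identical" follows both the nursery rhymes and the unlit device, and may simply mean apart from those two.

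**What stands.** Testing the package is legitimate, and nothing here faults the t-test. The conflict is narrow: it is between 7.5 and 7.2 and concerns the control arm's audio only. Section 9.0 sides with 7.2, and 5.0 is true of the active arm on either reading. What does not go away is that the purpose sentence in 1.0 is itself a statement of aim, names light alone, and sits beside a hypothesis that names two components. If 7.2 governs, the comparison does not serve that aim.

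**Stronger readings that the documents do not support.**

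- A reader might infer that 7.23 should be reduced by some audio effect. If effects were additive and the audio contributed a fixed 2.357 points, the lower limit for light would be 2.357 − 2.357 = 0. That figure is the interval's own lower limit, so it gives zero by construction and is no evidence about the audio. The documents give neither size nor sign for the audio effect.
- A reader might infer that the SAP attributes the result to light. Its available text does not, and the efficacy sentence directly follows the responder analysis, not the 7.23.
- A reader might infer that the arms were never defined in the SAP. Part of the SAP is not in the available text and may define them.

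**Conclusion.** The point holds as a limit on interpretation. If the arms were delivered as 5.0 and 7.2 describe, both the 7.23-point difference (95% CI 2.357 to 12.107) and the responder difference (87.5% against 35.7%) are results for light plus audio program versus sham plus nursery rhymes. They bear on the joint hypothesis in 1.0 and cannot be credited to light alone. If 7.5 describes what controls heard, the same numbers do address light, and it is the nursery-rhymes text and the joint hypothesis that misdescribe the comparison.

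The conclusion rests on the protocol wording, because the available SAP text does not say which audio was delivered. How much of 7.23 belongs to light cannot be calculated from these documents. The point should be fixed because it changes what the trial can conclude. Confidence is medium, given the unresolved conflict over the control audio and the SAP text that is not available.

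**What to change.** Reconcile 7.5 with 7.2 on the control arm's audio and state in the report which audio each arm heard, unless the unavailable part of the SAP already does so. Then follow one of two routes.

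- **The audio differed.** Restate the title, the purpose sentence in 1.0, the aim in 13.0 and the SAP's efficacy conclusion as light plus audio program versus sham plus nursery rhymes. Apply this to the t-test result and the responder analysis alike, and make no photobiomodulation-specific claim.
- **The audio was the same.** Correct the nursery-rhymes text in 7.2 and 9.0 and the joint hypothesis in 1.0. Section 5.0 can stand. The contrast may then be described as the effect of light, given alongside the audio program.

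Neither route needs new data, a new analysis or any change to 7.23. The cost is editing and, on the first route, a narrower claim than the title now suggests.
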